## 4 Study Procedures

### 4.1 Initial Study Assessments

- Objective assessments
  - Penile length – measured from pubic symphysis to glanular corona
- Subjective questionnaires (attached)
  - IIEF-15
  - Patient Disease History
  - Device usage diary provided for treatment group

### 4.2 Follow-up Visit – Treatment Group

- Questionnaire after penile traction, but before IPP surgery

### 4.3 Intra-op Variables and Follow-up Visits

- Objective assessments (intra-operative surgery)
  - Size of penile prosthesis implanted at time of surgery
  - Approach for implantation of penile prosthesis
  - Type of penile prosthesis implanted

- Any intra-operative complications of penile prosthesis surgery to be recorded by surgeon
- Follow-up visits - conducted per surgeon's individual protocols. May include one or more visits performed for up to 12 months after surgery.
  - Stretched penile length assessed
  - Notation of any interval complications or AEs

#### **4.4 Follow-up Surveys – Performed via Redcap Survey, Mailer or Telephone Follow-up**

- Performed at 3, 6, 12 months
- Subjective questionnaires for all patients (treatment and controls)
  - IIEF-15
  - Follow-up questionnaire
- Patients records to be reviewed 12 months post-operation to check for interval complications
  - Revision surgery, infection or hospitalizations

#### **4.5 Assessment of Length**

Penile length measurements will be obtained by a member of the clinical team using a measurement from the pubic symphysis to the corona of the glans penis. Measurements will be obtained pre-operatively and at all clinical visits post-operatively up to 12 months.

Size, type and approach of penile prosthesis implanted will be recorded by surgeon on operative note.

**See Attachments – Device Usage Diary, Disease Specific History, IIEF-15, Questionnaire After Penile Traction but before IPP Surgery, Follow Up Questionnaire**

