## Study Summary

Title	Penile Lengthening Pre-Penile Prosthesis Implantation
IRB Protocol Number	17-011052
Methodology	Open enrollment
Overall Study Duration	3 years
Subject Participation Duration	3 months
Objectives	Compare length of penile prosthesis inserted after traction therapy
Number of Subjects	80
Diagnosis and Main Inclusion Criteria	Men undergoing placement of a penile prosthesis
Study Device	RestoreX®, penile traction therapy
Duration of Exposure	Subjects will use device for 30 minutes, 3 times a day
Reference therapy	Use of the device will be compared against a control group using no traction therapy
Statistical Methodology	Statistical comparisons will be made comparing total length of prosthesis inserted between those using and not using traction, stratified by baseline penile length.

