# **2 Study Objectives**

## **2.1 Primary Objective**

1. The primary objective is to assess the length of the penile prosthesis inserted into subjects following completion of RestoreX® traction therapy compared to control groups (no treatment).

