### **3.5 Study Schema**

During the initial scheduled clinic appointment, the patient will receive a description of the study, and informed consent. Potential subjects will be notified about the two groups for the study: Treatment (PTT for 30 min 3x/day for 3 months) or No Treatment (control). Subjects planning to have their IPP procedure immediately and do not want to utilize traction therapy will be considered for the control group. Subjects who wish to wait for placement of IPP and are interested in utilizing traction will enter into the treatment group. Those consenting will receive initial study assessments and subjects who take part in the treatment group will be educated on how to use the device properly.

Patients will then be given a baseline questionnaire to complete and, if assigned to the treatment group, begin using the device. Patients in the treatment arm will record a daily journal of their usage of the device.

After 3 months (+1.5 months permitted), patients in the treatment arm will return for their scheduled procedure (control arm patients will undergo surgery without a 3-month delay). Only those who utilized the device for 3 months will be asked to complete a follow-up questionnaire at this time. Patients will also be encouraged to self-report any additional adverse events (AE's) that they encountered over the 3 months of using the therapy.

During surgery, data will be recorded by the surgeon to indicate type, length and approach taken for penile prosthesis implanted as well as any complications of penile prosthesis implantation. These complications may include urethral perforation, corporal perforation, device malfunction, bowel injury or vascular injury; all of which are standard potential complications of the surgery.

Following surgery, patients will be seen in the clinic based on the standard routine clinical practice. During these follow-up appointments, penile length measurements will be performed and recorded.

Patients will also be sent questionnaires by email or by mail (if email not available) at 3, 6, and 12 months post-operatively. If a patient has not returned their questionnaire within 2 weeks, a follow up phone call to the patient will be placed as a reminder. Alternatively, patients may answer the questions over the phone if that method is preferable.

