### 5.2 Statistical Analysis

Analyses will be performed using comparisons within patients of same baseline penile stretch length and between groupings of varying lengths. Comparison of device length implanted will be made for subjects using the traction device compared to those who did not utilize traction. Comparisons will also be made on other subjective and objective variables obtained including number of adverse events, complications, subjective responses to questionnaires, or other information. Pre- and post-operative penile lengths will also be compared within individuals. All data will be normalized based on pre-operative stretched penile length.

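### Baseline length is the only named adjuster between self-chosen arms, yet the plan does not require repeat readings or averaging; replicates would be a cheap improvement

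*Combined protocol and SAP*

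**What the plan says.** The primary objective (Section 2.1) is to "assess the length of the penile prosthesis inserted into subjects following completion of RestoreX® traction therapy compared to control groups". Allocation is by preference (Section 3.5): "Subjects planning to have their IPP procedure immediately and do not want to utilize traction therapy will be considered for the control group", and "Subjects who wish to wait for placement of IPP and are interested in utilizing traction will enter into the treatment group".

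The only variable named to make the arms comparable is length. The Study Summary says the comparison is "stratified by baseline penile length". Section 5.2 says: "Analyses will be performed using comparisons within patients of same baseline penile stretch length and between groupings of varying lengths". It gives no number or width of groups. It also says that data will be normalised by pre-operative stretched length, without a formula.

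On measurement, Section 4.1 defines the baseline value as "measured from pubic symphysis to glanular corona", and Section 4.5 has a clinical team member obtain it "using a measurement from the pubic symphysis to the corona of the glans penis". Neither calls it stretched, although Sections 4.3 and 5.2 use stretched length. Tables 1 and 2 mark one length assessment per arm, at baseline. The documents do not give the number of readings on that occasion, any averaging, a reliability estimate or a correction for measurement error.

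**The concern.** Because patients select their arm, true length may differ systematically between arms; concern about length is a plausible reason to accept a lengthening device and a delay. Adjustment for length is meant to remove that difference. A reading with random error removes only part of it, even if the reading is unbiased and the rater does not know the group.

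The remainder goes into the estimated traction effect on implanted length. If shorter men choose traction, it hides a real gain; if longer men do, it creates an apparent one. More patients do not reduce it. The trial could not estimate the reliability of its own baseline reading unless replicates were recorded.

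**Working it through.** **Inputs from the documents.** Allocation is self-chosen (Section 3.5). The adjuster is length (Study Summary, Section 5.2). Accrual is 40 per arm, for at least 20 completers per arm (Section 3.4), so 20 to 40 per arm is the range to examine. The pilot gains cited in Section 1.1 are +0.9 and +1.6 cm; they are changes in penile length, not implant length. The documents give no reliability, slope, SD, target effect or significance level, so there is no figure of the plan's own to reproduce.

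**Assumed inputs.** Slope of implant length on true length β = 1; true arm difference D = 0.5 or 1 cm; within-arm reliability λ of one reading = 0.7 to 0.9; no traction effect. For the error rates: SD of true length 1.5 cm, residual SD 1.2 cm, two-sided 5% test.

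**Formulas.** When the comparison conditions on the reading (regression or fine strata):

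- bias = β × (1 − λ) × D
- reliability of the mean of k independent readings: λ_k = kλ / (1 + (k − 1)λ)

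Example at λ = 0.7, D = 1 cm: one reading leaves 1 × 0.30 × 1 = 0.30 cm. For two readings, λ_2 = 1.4/1.7 = 0.824, which leaves 0.18 cm. For three, λ_3 = 2.1/2.4 = 0.875, which leaves 0.13 cm.

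Size of bias in cm for D = 1 cm (D = 0.5 cm in brackets):

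| Reliability of one reading | One reading | Mean of two | Mean of three |
|---|---|---|---|
| 0.7 | 0.30 (0.15) | 0.18 (0.09) | 0.13 (0.06) |
| 0.8 | 0.20 (0.10) | 0.11 (0.06) | 0.08 (0.04) |
| 0.9 | 0.10 (0.05) | 0.05 (0.03) | 0.04 (0.02) |

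The relative reduction from a second reading is λ/(1 + λ): 0.7/1.7 = 41% and 0.9/1.9 = 47%. A smaller slope scales the bias down: at β = 0.7, λ = 0.8 and D = 1 cm it is 0.7 × 0.2 = 0.14 cm.

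**Simulation checks.**

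- Baseline-adjusted regression reproduced the formula. At λ = 0.8 and D = 1 cm the mean bias was 0.19 to 0.20 cm in size at 20, 40 and 400 per arm, so it does not shrink with n. Strata 0.5 cm wide gave 0.21 cm.
- False-positive rates, one reading versus the mean of two (repeat runs differ by up to about one percentage point):
  - λ = 0.7, D = 1 cm: about 14% versus 8% at 40 per arm; about 9% versus 6% at 20 per arm
  - λ = 0.7, D = 0.5 cm, 20 per arm: about 6% versus 5%
  - λ = 0.9, D = 1 cm, 40 per arm: about 6% versus 5%
- Change score (implant length minus baseline reading): at β = 1 the bias is about 0.00 cm and the error rate about 5%, whatever the reliability. At β = 0.7 it is about 0.30 cm, again whatever the reliability, because 0.3 × D is then over-subtracted.
- Coarse groups with perfect measurement (D = 1 cm, β = 1, residual SD 1 cm): tertiles leave about 0.20 cm and a median split about 0.37 cm.

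**The case against.** A reader might infer that the protocol prescribes one unreplicated reading. It does not. In Section 4.5 the phrase quoted above sets the landmarks, not a count, and the tables show one occasion rather than one reading. What can be said is that the number is unstated, so a single reading is permitted.

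A reader might also infer that a fixed share of any arm difference must end up in the result. That holds only when the analysis conditions on length. The stratified and within-length comparisons in the Study Summary and Section 5.2 do so, but the normalisation in Section 5.2 is undefined. Read as a change score at slope 1, it would leave no bias from random error. This part of the objection stands, although a change score is not a safe default if the slope differs from 1.

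The size is also open to challenge. Reliability, slope and arm difference are all assumed, and a 1 cm gap is 0.67 of the assumed SD (1/1.5). At the planned minimum of 20 completers, or with a smaller gap or better reliability, the excess false-positive rate is small. Coarse length groups can leave as much bias or more, and confounding by factors other than length is untouched by replicates. Same-visit repeats remove only within-visit error; day-to-day error and error shared by one rater stay. All of this limits the priority of the point. None of it is a reason to leave the number of readings open.

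One possible escape looks unlikely. If men chose their arm on the study reading itself, the regression bias would be near zero; but Section 3.4 places that reading after consent.

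**Conclusion.** The point holds conditionally. The documents show self-chosen arms, length as the sole named adjuster, one scheduled pre-operative assessment and no requirement for replication or averaging. If one reading is used and the analysis conditions on it, under-adjustment follows and sample size does not cure it.

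Under the stated assumptions the bias is about 0.05 to 0.30 cm, or 6% to 33% of the pilot's +0.9 cm (0.05/0.9 and 0.30/0.9). That ratio is only for scale, since the pilot measured a different quantity. The direction depends on which men choose traction, which the documents do not show. The missing word 'stretched' in Sections 4.1 and 4.5 is a separate gap in definition, worth closing in the same edit.

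This is a low-cost improvement, not a demonstrated error in the plan.

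**What to change.** - **Sections 4.1 and 4.5:** state that baseline length is stretched length. Take it two or three times at the baseline visit, repositioning between readings, and record each reading.
- **Section 5.2:** use the mean of those readings as the baseline value and enter it as a continuous covariate in the primary comparison of implanted length. State what normalised means, so that it does not compete with this analysis.
- **Sensitivity analysis:** correct the baseline adjustment for measurement error over a range of reliabilities. Treat the estimate from the replicates as an upper bound, because same-visit repeats miss day-to-day and shared rater error.

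Cost: about a minute per man at a visit already held, one or two extra form fields and one additional analysis. The downside is a slightly longer visit. No extra staff or new procedure is needed.

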### **3.4 Consent and Accrual**

During the patient's consultation appointment, they will receive a description of the study and if the patient expresses interest in participating, a formal consent will be reviewed (see **Attachment – Consent Form**).

If the patient successfully completes the consenting process, they will undergo initial study penile length assessments (described later in the protocol). Those wishing additional time to consider participation may be rescheduled to a later date if desired.

At the time of consent, all participants will be assigned a study identifier, with a master list maintained in a password protected database (Mayo server) linking the patient to the identifier. A total of 40 patients will be accrued into each arm of the study, for a total of 80 patients accrued overall. It is estimated that 80 patients will need to be accrued in order to achieve a minimum of 20 subjects in each arm that will complete the study from start to finish.

No limitations will be applied to either clinical site for enrollments, such that it is possible that one clinical site may enroll 100% of the patients.

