### 8.2 Conflict of Interest

[name] is the inventor and developer of the RestoreX® device. His conflict has previously been reviewed with the Mayo Clinic Conflict of Interest Review Board, and following review, it has been determined that [name] is able to conduct these studies as a Primary Investigator.

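### The primary outcome is an implant length recorded by a surgeon who very likely knows the group, and the plan allows only indirect checks for differential sizing.

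*Combined protocol and SAP*

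**What the plan says.** Section 2.1 sets the primary objective: to "assess the length of the penile prosthesis inserted into subjects following completion of RestoreX® traction therapy", compared with untreated controls. Two places say who records that length. Section 3.5 has "During surgery, data will be recorded by the surgeon to indicate type, length and approach taken for penile prosthesis implanted", and section 4.5 has "Size, type and approach of penile prosthesis implanted will be recorded by surgeon on operative note".

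The Study Summary describes the methodology only as "Open enrollment". Under section 3.5 men select their own group: "Subjects who wish to wait for placement of IPP and are interested in utilizing traction will enter into the treatment group". Those who want surgery at once without traction are considered for the control group. No blinding of surgeon, patient or measurer is described anywhere.

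The intra-operative list in section 4.3 covers implant size, approach, type and complications. It has no measurement on which the size was based. For penile length, section 4.5 says only: "Penile length measurements will be obtained by a member of the clinical team". Tables 1 and 2 in section 4.6 list a length assessment at baseline and at no other time, although sections 4.3 and 4.5 also call for length at post-operative visits. Section 5.2 normalizes all data to pre-operative stretched length and has no surgeon or site term.

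Section 8.2 states that a named individual "is the inventor and developer of the" device and has been cleared to act as Primary Investigator after a conflict-of-interest review. Section 3.4 sets no site limit, so that "it is possible that one clinical site may enroll 100% of the patients".

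**The concern.** If the surgeon selects the implant, its length reflects a judgement as well as anatomy. A surgeon who knows that a man has completed three months of traction, and expects a gain, may settle on a longer implant in a borderline case. The primary comparison could then favour traction with no true lengthening. The data listed in the plan would not directly separate the two explanations.

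The length used for normalization raises a similar worry. If whoever measures it knows or expects the man's group, error in that measurement passes into the normalized primary outcome.

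The stakes are higher because the inventor may lead the trial and one site may supply every patient. A positive result would invite the question of differential sizing, and the trial would have little with which to answer it.

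**Working it through.** **1. Is the surgeon likely to know the group?** The documents do not say so outright. The inference is strong. Physicians recruit from their own practices (section 3.3), men choose their group openly, and treated men return after three months (up to 1.5 months more permitted) while controls have no such delay (section 3.5). That the surgeon chooses the size is also an inference, since the text says only that the surgeon records it.

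**2. What could reveal differential sizing?**

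| Recorded item | Where | Limit as a check |
|---|---|---|
| Intra-operative complications, including corporal and urethral perforation | 3.5, 4.3 | Recorded by the same surgeon; probably few events with 20 to 40 men per arm |
| Revision, infection, hospitalization to 12 months | 3.5, 4.4 | Indirect; probably few events |
| Post-operative stretched length | 4.3, 4.5 | No masking; visits follow each surgeon's own protocol; measured with the implant in place, so a longer implant may itself affect it |
| Pre-operative length | 4.5, 4.6 | Scheduled at baseline only; for treated men that is before traction |

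Section 4.5 calls for length pre-operatively, but this does not settle whether treated men are measured again after traction. If they are not, no step shows tissue gain before the implant is selected.

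**3. The plan's own figure.** Section 3.4 accrues 40 per arm to obtain at least 20 completers per arm. The implied loss is 1 − 20/40 = 50%, and 20/(1 − 0.50) = 40 per arm, 80 in total. This reproduces, but the 50% is derived from the same two numbers, so it checks the arithmetic only. The plan gives no SD, effect size, alpha or power.

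**4. Illustration of size.** All of these are assumptions: one size step is 1 cm; 25% to 50% of treated men are sized up by one step; SD 1.5 to 2.0 cm; no true effect; two-sided 5% unadjusted t-test.

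- Shift: 0.25 × 1 = 0.25 cm to 0.50 × 1 = 0.50 cm.
- Standard error: SE = SD × √(2/n). For n = 20 and SD 1.5, SE = 1.5 × √0.1 = 0.474 cm.
- Noncentrality: shift/SE. For 0.50 cm, 0.50/0.474 = 1.05.
- Chance of a significant result: both tails of the noncentral t with 2n − 2 degrees of freedom.

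| n per arm | SD (cm) | Shift 0.25 cm | Shift 0.50 cm |
|---|---|---|---|
| 20 | 1.5 | 8.1% | 17.7% |
| 20 | 2.0 | 6.7% | 12.0% |
| 40 | 1.5 | 11.4% | 31.3% |
| 40 | 2.0 | 8.6% | 19.7% |

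At SD 2.5 cm and a 0.50 cm shift, the figures are 9.5% (20 per arm) and 14.3% (40 per arm). For a given shift the rate rises with sample size, so recruiting more men would not cure the problem.

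**The case against.** Implant length is a deliberate endpoint: section 1.3 regards it as clinically more relevant than penile length. With immediate surgery in one group and a three-month wait in the other, masking the surgeon is hardly practical. Both points stand, and they are reasons to add a check rather than change the endpoint.

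A reader might infer that nothing in the data could reveal differential sizing. The documents do not support that. Complications, revisions and post-operative length are recorded, and section 5.2 compares complications between groups and length within individuals. Longer implants without matching post-operative length, or with more perforations, would be a signal, though a weak one.

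A reader might also infer that the inventor implants every device. Section 8.2 says only that the inventor may be Primary Investigator. Names are removed, and no passage states who operates. The combination is possible under the plan but not shown.

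Nor does unmasked post-operative measurement enter the normalization of the primary outcome. Section 5.2 normalizes on pre-operative length alone, and post-operative length belongs to a secondary objective (section 2.2).

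The remedies have limits too. An intra-operative measurement would be made by the same unblinded surgeon, so it would expose sizing up after measurement but not generous measurement. A split by surgeon is impossible if one surgeon treats everyone. Otherwise it is imprecise and mixes surgeon with case mix. These limits must be stated with the fix, but they do not remove its value.

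**Conclusion.** The point holds in a limited form. The primary outcome is recorded by a surgeon who very likely knows the group. No measurement underlying the chosen size and no masked or independent length assessment is specified. No length is scheduled between traction and implantation. Differential sizing can therefore be checked only indirectly.

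Its actual size cannot be derived from the documents. The ranges of 6.7–17.7% (20 per arm) and 8.6–31.3% (40 per arm) show what an assumed shift of 0.25–0.50 cm would do at an assumed SD of 1.5–2.0 cm. It would be tempting to read them as the trial's error rate, but that is not supported. The unadjusted t-test is not the planned analysis, which stratifies and normalizes by baseline length, and with self-selected groups a nominal 5% is not assured even without sizing bias. The direction is firmer than the magnitude: sizing up after traction would favour traction, and a larger sample would make a false positive from it more likely.

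**What to change.** 1. **Intra-operative record.** Where the surgeon measures before choosing a size, enter that measurement before the implant is selected. Report implanted size minus measured length by arm as a check, and measured length as a supportive endpoint. State that this detects sizing up after measurement, not biased measurement by the same surgeon. The plan does not say that surgeons measure first, so this should be confirmed. The field has to be in place before surgery, because unrecorded measurements may not be recoverable.
2. **Length measurements.** Take the baseline length used for normalization before the man's group is settled. Where feasible, have post-operative lengths, a secondary outcome, taken by an existing team member who is not told the group.
3. **Reporting.** If more than one surgeon contributes patients, show the primary difference by surgeon, descriptively.

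The cost is one extra field, an instruction on who measures and when, and one additional line of results, with no new staff. Masking will be imperfect, and the by-surgeon split may be imprecise or unavailable. No sizing rule is proposed.
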